7.2.3. Liver-related Laboratory Evaluations

Liver-related abnormalities after initial study drug dosing will be examined and summarized using the number and EAIR of subjects who were reported to have the following central laboratory test values for postbaseline measurements:

- AST: (a) > 3 times of the upper limit of reference range (ULN); (b) > 5 x ULN; (c) > 10 x ULN; (d) > 20 x ULN
- ALT: (a) > 3 x ULN; (b) > 5 x ULN; (c) > 10 x ULN; (d) > 20 x ULN
- AST or ALT: (a) > 3 x ULN; (b) > 5 x ULN; (c) > 10 x ULN; (d) > 20 x ULN
- Total bilirubin: (a) > 1 x ULN; (b) > 2 x ULN
- ALP: > 1.5 x ULN
- AST or ALT > 3 x ULN and (a) total bilirubin > 1.5 x ULN; (b) total bilirubin > 2 x ULN; (c) total bilirubin > 2 x ULN and ALP < 2 x ULN

The summary will include data for the following exposure periods for SEL and placebo exposures, respectively:

- SEL exposure: at any time point after the first dosing date of Run-in SEL, up to and including the date of last dose of SEL plus 30 days.
- Placebo exposure: at any time point on or after Study Day 31, up to and including the date of last dose of Randomized placebo plus 30 days.

For individual laboratory tests, subjects will be counted once based on the most severe values in corresponding period. For both the composite endpoint of AST or ALT and total bilirubin, subjects will be counted once when the criteria are met at the same postbaseline visit date. A listing of subjects who met at least 1 of the above criteria will be provided.

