- 8) Male subjects must refrain from sperm donation from the Screening visit through 30 days following the last dose of study drug
- 9) Female subjects must refrain from egg donation or harvest from the Screening visit through 30 days following the last dose of study drug
- 10) Subjects must refrain from blood product donation from the Screening visit through 30 days following the last dose of study drug
- 11) Mean systolic blood pressure (SBP) must be < 160 mmHg and mean diastolic blood pressure (DBP) must be < 100 mmHg taken at two time-points at least five minutes apart within 30 days prior to Enrollment (Visit A)
- 12) Required baseline laboratory data, analyzed by central laboratory, within 30 days prior to Enrollment (Visit A) as shown in the table below

Organ System	Parameter	Required Value
Hematologic	WBC, neutrophil, lymphocyte, and platelet count	$\geq 0.75 \times \text{LLN}$ to $\leq 1.5 \times \text{ULN}$
Hepatic	Serum total bilirubin	$\leq 1.5 \times \text{ULN}$
	Serum ALT	
	Serum AST	

Organ System	Parameter	Required Value
Pregnancy	β -HCG ^a	Negative
Infection	HIV ^b	Negative HIV antibody
	HBV	Negative HBsAg and negative HBc antibody or positive HBc and negative for HBV DNA by quantitative PCR
	HCV	Negative HCV antibody or negative viral RNA (if HCV antibody is positive)

a For women of childbearing potential only; serum β -HCG must be negative during Screening

b If screening test is positive, a negative confirmatory test will be required for eligibility

Abbreviations: β -HCG = beta human chorionic gonadotropin, ALT = alanine aminotransferase, AST = aspartate aminotransferase, DNA = deoxyribonucleic acid, LLN = lower limit of normal, HBc antibody = anti-hepatitis B core antibody, HBsAg = hepatitis B surface antigen, HBV = hepatitis B virus, HCV = hepatitis C virus, HIV = human immunodeficiency virus, PCR = polymerase chain reaction, RNA = ribonucleic acid, ULN = upper limit of normal, WBC = white blood count

- 13) Have either a normal 12-lead electrocardiogram (ECG) or an ECG with abnormalities that are not considered to be clinically significant by the investigator within 30 days prior to Enrollment (Visit A)
- 14) In the judgment of the investigator, participation in the study offers an acceptable benefit to risk ratio, taking into consideration the subject's current DKD status, medical condition, and the potential benefits and risks of alternative treatments for DKD

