7.1.6.1. Calculation of Treatment Exposure

Treatment exposure will be calculated as follows, for SEL and placebo respectively:

- SEL: Total exposure (Patient Year) is calculated as the sum of Run-in SEL and Randomized SEL exposure time (in years) for all subjects who have been exposed to Run-in SEL and/or Randomized SEL in the Safety Analysis Set, starting from the first dosing date of Run-in SEL to the last dosing date of SEL (Run-in SEL or Randomized SEL).

In other words,

Total SEL Exposure

$$\begin{aligned}
 &= \sum_{i \in \{\text{Subjects randomized to SEL}\}} \text{Ex}(\text{first dose of Runin SEL to last dose of Randomized SEL})_i \\
 &+ \sum_{i \in \{\text{Subjects randomized to Placebo}\}} \text{Ex}(\text{first dose of Runin SEL to last dose of Runin SEL})_i \\
 &+ \sum_{i \in \{\text{Subjects not randomized}\}} \text{Ex}(\text{first dose of Runin SEL to last dose of Runin SEL})_i
 \end{aligned}$$

- Placebo: Total exposure (Patient Year) is calculated as the sum of Randomized placebo exposure time (in years) for all subjects who exposed to Randomized placebo in the Safety Analysis Set, starting from Study Day 1 to the last dosing date of Randomized placebo.

In other words,

Total Placebo Exposure

$$= \sum_{i \in \{\text{Subjects randomized to Placebo}\}} \text{Ex}(\text{first dose of Randomized Placebo to last dose of Randomized Placebo})_i$$

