7.2.2.1. Treatment-Emergent Laboratory Abnormalities

Treatment-emergent laboratory abnormalities are defined as follows for SEL and placebo exposures, respectively. Treatment-emergent laboratory abnormalities will only be evaluated for central laboratory testing results.

- SEL exposure: values that increase at least 1 toxicity grade from Baseline at any time point after the first dosing date of Run-in SEL, up to and including the date of last dose of SEL plus 30 days.
- Placebo exposure: values that increase at least 1 toxicity grade from Baseline at any time point on or after Study Day 31, up to and including the date of last dose of Randomized placebo plus 30 days.

Baseline is defined as the last nonmissing value prior to the first dose of Run-in SEL.

If the relevant Baseline laboratory value is missing, any abnormality of at least Grade 1 observed within the time frame specified above will be considered treatment emergent.

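### Two rows of the liver table (bilirubin above 1 x ULN, ALP above 1.5 x ULN) ignore Baseline status, and the exposure-adjusted rate turns elevations already present at entry into a partly artificial selonsertib excess

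*SAP*

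**What the plan says.** SAP 7.2.3 summarizes the number and exposure-adjusted incidence rate (EAIR) of subjects "reported to have the following central laboratory test values for postbaseline measurements". The rows are absolute multiples of ULN. Two have low thresholds: the first part of "Total bilirubin: (a) > 1 x ULN; (b) > 2 x ULN", and a single ALP row at 1.5 x ULN. Neither refers to the subject's Baseline value.

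The observation windows are:
- "SEL exposure: at any time point after the first dosing date of Run-in SEL, up to and including the date of last dose of SEL", extended by 30 days.
- For placebo, a window that opens at Study Day 31 and closes 30 days after the final dose of Randomized placebo.

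The Safety Analysis Set (SAP 3.1.5) is everyone with at least one dose of Run-in SEL. Under SAP 7.1.6.1 the SEL denominator sums exposure "for all subjects who have been exposed to Run-in SEL and/or Randomized SEL in the Safety Analysis Set". Placebo-randomized and never-randomized subjects therefore contribute only their run-in SEL time to it. The placebo denominator is Randomized placebo time alone. SAP 7.1.6.2 divides subjects with at least one event by that exposure.

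Protocol 4.2, criterion 12, has a hepatic row headed by "Serum total bilirubin" with a limit of 1.5 x ULN. ALT and AST stand in the same row; ALP is not in the table.

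The neighbouring rule in SAP 7.2.2.1 does use Baseline: it counts "values that increase at least 1 toxicity grade from Baseline at any time point after the first dosing date of Run-in SEL". SAP 7.2.2.2 requires a rise of two grades.

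**The concern.** A subject with bilirubin at 1.2 x ULN from screening onward is eligible, and is counted at the first sample after Run-in SEL although nothing has changed on drug.

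In an ordinary parallel-group table, randomization would spread such subjects evenly and the rates would stay comparable. Here it cannot. A placebo-randomized subject with a persistent elevation is counted once under SEL and once under placebo, but brings only about four to six weeks to the SEL denominator. A never-randomized subject with a postbaseline sample is counted under SEL only.

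The fault is the combination. Without a Baseline condition the rows admit pre-existing elevations, and the EAIR construction then loads them onto SEL. It is separate from the spacing of blood draws and from the Day 31 start of the placebo window, because it arises even with equal sampling and equal windows.

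Liver injury is a potential risk named in Protocol 1.6 and 7.5.4. A built-in excess could be mistaken for a signal, or could lead readers to discount a real one.

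**Working it through.** SAP 7.2.3 gives no numeric result, so there is no figure to reproduce. The check applies the SAP's own EAIR definition to a drug with no liver effect.

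**Inputs from the documents**
- n = 150 per arm (SAP 1.3).
- Run-in SEL time r = 28 to 42 days: 21–28 days from Visit B to Visit C plus 7–14 days to Visit 1 (Protocol Appendix 2). The midpoint is 35 days.
- Mean randomized treatment T from 48 weeks (the minimum in Protocol 3.3) to 84 weeks (the endpoint horizon in SAP 6.1.1), equal in both arms.

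**Assumptions, not in the documents**
- Share p of subjects with an entry elevation that persists: 1% to 10%.
- Number of never-randomized subjects: 0, 30 or 60, each with a postbaseline sample.
- New-onset rate λ = 3 per 100 patient-years (PY), the same on SEL and placebo.

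**Step 1: pre-existing cases only, no non-randomized subjects**
- SEL rate = 2np / (nT + 2nr).
- Placebo rate = np / (nT).
- Ratio = 2T / (2r + T). Both p and n cancel, and the ratio exceeds 1 whenever T > 2r. At most 2r is 84 days, or 12 weeks.

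| T | r | Ratio |
|---|---|---|
| 336 days (48 weeks) | 28 days | 672/392 = 1.71 |
| 336 days | 42 days | 672/420 = 1.60 |
| 588 days (84 weeks) | 28 days | 1176/644 = 1.83 |
| 588 days | 42 days | 1176/672 = 1.75 |

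As rates with p = 5% and r = 35 days:
- T = 48 weeks: 15/166.7 PY = 9.00 per 100 PY on SEL against 7.5/138.0 PY = 5.44 on placebo; ratio 1.66 before rounding.
- T = 84 weeks: 15/270.2 PY = 5.55 against 7.5/241.5 PY = 3.11; ratio 1.79.

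**Step 2: add non-randomized subjects**
- With g = never-randomized/n and full run-in time for each, ratio = (2+g)T / ((2+g)r + T). Thirty subjects (g = 0.2) give 1.73 to 1.99 over the same ranges of r and T.
- Upper case: 60 subjects with 0.06 years each, r = 35 days (0.0958 years), T = 1.4 years. SEL exposure is 150 x 1.4958 + 150 x 0.0958 + 60 x 0.06 = 242.3 PY, and placebo exposure is 210 PY. Ratio = (360/242.3)/(150/210) = 2.08.

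**Step 3: add equal new onset (r = 35 days, no non-randomized subjects)**
- SEL cases = 2np + (1−p)n[(1−e^(−λ(T+r))) + (1−e^(−λr))].
- Placebo cases = np + (1−p)n(1−e^(−λT)).

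Rates per 100 PY, SEL against placebo, with the ratio:

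| p | T = 48 weeks | T = 84 weeks |
|---|---|---|
| 1% | 4.73 vs 4.02 (1.18) | 4.01 vs 3.52 (1.14) |
| 5% | 11.81 vs 8.25 (1.43) | 8.33 vs 5.89 (1.42) |
| 10% | 20.65 vs 13.53 (1.53) | 13.74 vs 8.85 (1.55) |

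**Step 4: subjects at or below the threshold at Baseline**

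With pre-existing cases removed, the rates are 2.96 vs 2.96 (48 weeks) and 2.93 vs 2.93 (84 weeks); the ratio is 1.00. Restricting both numerator and denominator to this stratum leaves these rates unchanged, since (1−p) cancels. The calculation sets aside the separate mismatch between the Day 31 placebo window and the Day 1 start of placebo exposure.

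**The case against.** Four points can fairly be made for the plan.

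- **Absolute thresholds are a conservative screen, and Baseline-aware displays are already planned.** SAP 7.2.1 gives change from Baseline and line plots for bilirubin and ALP, SAP 7.2.2.3 tabulates treatment-emergent grade increases, and subjects meeting any liver criterion are listed. A stable 1.2 x ULN would show there as no change. This lessens the problem, but it does not correct the rates in this table, which a reader will take as comparable between columns.
- **The table is descriptive.** SAP 7.2 plans no formal testing. This stands, and it limits the consequence to interpretation.
- **Investigators can keep out concerning abnormalities.** Exclusion 18 and randomization criterion 7 allow this. It is discretionary, and a stable mild elevation need not trigger it.
- **Dropping already-elevated subjects could hide worsening.** This stands. With only one ALP threshold, a rise from 1.6 to 4 x ULN would vanish from the count, and a bilirubin rise from 1.05 to 1.9 x ULN would leave the lower row without reaching the upper one. The remedy must therefore separate these subjects, not remove them.

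A reader might also infer that the whole liver table is compromised. The documents do not support that. Entry caps bilirubin, ALT and AST at 1.5 x ULN, so the AST/ALT rows from 3 x ULN upward, the bilirubin row above 2 x ULN and the combined rows are largely protected.

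**Conclusion.** The point holds for two rows: total bilirubin above 1 x ULN and ALP above 1.5 x ULN. For elevations that are present at entry and persist, the SAP's definitions give a SEL/placebo EAIR ratio of about 1.6 to 1.8 with no drug effect and no non-randomized subjects. The ratio reaches about 2.1 with 60 assumed non-randomized subjects and the longer treatment time. For these cases alone it does not depend on prevalence.

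A reader might infer that the table will show an excess of that size, or one that is entirely pre-existing. Neither follows. Those ratios assume full persistence and no new onset, and the documents give no entry prevalence for either test. With equal new onset at 3 per 100 PY and prevalence of 1% to 10%, the overall ratio is about 1.14 to 1.55. At 1% prevalence the pre-existing cases are about 3 under SEL against 1.5 under placebo. The supportable conclusion is that part of any apparent SEL excess in these two rows may be pre-existing, and that the table as specified cannot show how much.

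**What to change.** In SAP 7.2.3, for these two rows only:

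1. Present number and EAIR separately by Baseline status (last value before the first Run-in SEL dose at or below the threshold, or above it), each with its own exposure denominator.
2. Base the SEL versus placebo comparison on subjects at or below the threshold at Baseline.
3. For subjects above it at Baseline, show a shift from Baseline to the maximum postbaseline value within each exposure, with bands high enough for worsening to stay visible.
4. Treat a missing Baseline as in SAP 7.2.2.1, so that such a subject's elevation still counts as emergent.
5. Keep the planned listing of subjects meeting any criterion, and leave the other rows as they are.

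The cost is a few sentences in the SAP, one Baseline flag in the program and a few more table rows. No new data are needed.

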7.3. Vital Signs and BMI

Descriptive statistics (n, mean, SD, median, Q1, Q3, minimum, and maximum) will be provided by treatment group for vital signs and BMI as follows. Body weight will be summarized as described in Section 5.1.

- Baseline value
- Value at each postbaseline visit
- Change from Baseline at each postbaseline visit

A Baseline value will be defined as the last available value collected on or prior to the date of first Run-in SEL administration. Change from Baseline to a postbaseline visit will be defined as the postbaseline value minus the Baseline value.

In the case of multiple values in an analysis window, data will be selected for analysis as described in Section 3.8.3. No inferential statistics will be generated.

7.4. Prior and Concomitant Medications

Medications collected at screening and during the study will be coded using the current version of the World Health Organization (WHO) Drug dictionary.

7.4.1. Prior Medications

Prior medications are defined as any medications taken before a subject took the first Run-in SEL.

Prior medications will be summarized by preferred name using the number and percentage of subjects for each treatment group and overall. A subject reporting the same medication more than once will be counted only once when calculating the number and percentage of subjects who received that medication. The summary will be ordered by preferred term in order of descending overall frequency. For drugs with the same frequency, sorting will be done alphabetically.

For the purposes of analysis, any medication with a start date prior to the first dosing date of Run-in SEL will be included in the prior medication summary regardless of when the stop date is. If a partial start date is entered the medication will be considered prior unless the month and year (if day is missing) or year (if day and month are missing) of the start date are after the first dosing date of Run-in SEL. Medications with a completely missing start date will be included in the prior medication summary, unless otherwise specified.

Summaries will be based on the Safety Analysis Set. No formal statistical testing is planned.

All prior medications will be provided in a listing sorted by subject ID number and start date in chronological order.

Disease-specific prior medications (ACEi, ARB, and ARB or ACEi) will be summarized and listed in a similar manner.

Prior use of SGLT-2 inhibitors, statins and GLP1-RAs will also be summarized and listed in a similar manner.

7.4.2. Concomitant Medications

Concomitant medications are defined as medications taken while a subject took study drug. Use of concomitant medications will be summarized by preferred name using the number and percentage of subjects for each treatment group and overall. A subject reporting the same medication more than once will be counted only once when calculating the number and percentage of subjects who received that medication. The summary will be ordered by preferred term in descending overall frequency. For drugs with the same frequency, sorting will be done alphabetically.

For the purposes of analysis, any medications with a start date prior to or on the first dosing date of Run-in SEL and continued to be taken after the first dosing date, or started after the first dosing date but prior to or on the last dosing date of study drug will be considered concomitant medications. Medications started and stopped on the same day as the first dosing date of Run-in SEL or the last dosing date of study drug will also be considered concomitant. Medications with a stop date prior to the date of first dosing date of Run-in SEL or a start date after the last dosing date of study drug will be excluded from the concomitant medication summary. If a partial stop date is entered, any medication with the month and year (if day is missing) or year (if day and month are missing) prior to the date of first Run-in SEL administration will be excluded from the concomitant medication summary. If a partial start date is entered, any medication with the month and year (if day is missing) or year (if day and month are missing) after the study drug stop date will be excluded from the concomitant medication summary. Medications with completely missing start and stop dates will be included in the concomitant medication summary, unless otherwise specified.

Summaries will be based on the Safety Analysis Set. No formal statistical testing is planned.

All prior and concomitant medications (other than per-protocol study drugs) will be provided in a by-subject listing sorted by subject ID number and administration date in chronological order.

Disease-specific concomitant medications (ACEi, ARB, and ARB or ACEi) will be summarized and listed in a similar manner.

Concomitant use of SGLT-2 inhibitors, statins and GLP1-RAs will also be summarized and listed in a similar manner.

7.5. Electrocardiogram Results

ECG analysis results are intended to identify meaningful changes in the QT interval. If potential abnormalities of interest are identified, further analyses may be conducted. Summaries of investigator assessment of ECG readings will be provided for the Safety Analysis Set for each scheduled time point. No formal statistical testing is planned.

7.5.1. Investigator Electrocardiogram Assessment

A shift table of the investigators' assessment of ECG results at each postbaseline visit compared with Baseline values will be presented by randomization status and treatment group using the following categories: normal; abnormal, not clinically significant; abnormal, clinically significant; or missing. Baseline ECG value will be defined as the last nonmissing value before the first dose of Run-in SEL. The number and percentage of subjects in each cross-classification group of the shift table will be presented. Subjects with a missing value at Baseline or postbaseline will not be included in the denominator for percentage calculation. No formal statistical testing is planned.

A by-subject listing for ECG assessment results will be provided by subject ID number and visit in chronological order.

7.5.2. Corrected QT Intervals

The QT interval (measured in millisecond [msec]) is a measure of the time between the start of the Q wave and the end of the T wave in the heart's electrical cycle. The QT interval represents electrical depolarization and repolarization of the ventricles. The QT interval is affected by heart rate, and a number of methods have been proposed to correct QT for heart rate.

Corrected QT (QTc) intervals will be derived using Fridericia's correction (QTcF) as follows:

$$QT_{cF} = \frac{QT}{\sqrt[3]{RR}}$$

where QT is measured in msec; RR = 60/Heart Rate (beats per min [bpm]) and RR is measured in seconds

The maximum postbaseline QTcF interval values obtained during the study will be summarized within the following categories:

- > 450 msec
- > 480 msec
- > 500 msec

The maximum postbaseline change in QTcF interval values obtained during the study will also be summarized within the following categories:

- > 30 msec
- > 60 msec

QTcF and uncorrected QT values at each visit and change from Baseline at each visit will be summarized for the Safety Analysis Set by treatment group and randomization status using descriptive statistics.

7.5.3. PR and QRS Intervals

The PR interval (measured in msec) is a measure of the time between the start of the P wave (the onset of atrial depolarization) and the beginning of the QRS complex (the onset of ventricular depolarization). The QRS interval measures the duration of the QRS complex. The maximum postbaseline ventricular rate (VR) and PR and QRS intervals observed during the study will be categorized. The number and percentage of subjects having values in the following ranges will be presented by treatment group and randomization status:

- VR > 100 bpm
- PR interval > 200 msec
- QRS interval > 110 msec

In addition, VR, PR, RR, and QRS values at each visit and change from Baseline at each visit will be summarized for the Safety Analysis Set by treatment group and randomization status using descriptive statistics.

7.6. Other Safety Measures

7.6.1. Pregnancy Report

A data listing will be provided for subjects experiencing pregnancy during the study, from screening to subjects' last study visit.

7.6.2. HIV-1, HBV, and HCV Serology

Data for HIV-1, HBV, and HCV serology will be listed and summarized.

7.6.3. Digoxin and C-Peptide Testing Results

A data listing will be provided for digoxin levels; a separate listing will be provided for C-peptide testing results.

